9.4.7. Pharmacokinetic/Pharmacodynamic Analyses

All patients who have received at least 1 dose of study treatment and at least 1 post baseline evaluable PK sample will be included in the PK analysis population.

Abemaciclib, irinotecan, and temozolomide concentrations will be summarized by analyte using descriptive statistics. Additional analyses utilizing the population PK approach may also be conducted if deemed appropriate. Relationships between exposure and measures of efficacy and safety may be explored.

9.4.8. Subgroup Analyses

Subgroup analyses for PK, efficacy, and safety will be performed by method of administration (whole administration and alternative administration) of study drug when applicable.

9.4.9. Product Acceptability and Palatability

Responses from the drug product acceptability and palatability questionnaires for tablet and oral granules swallowed whole, dispersed in food or liquid, or dispersed and administered through a nasogastric or gastrostomy tube will be summarized categorically (frequency and percentage) by age group, for each visit separately and in aggregate. In addition, general trends in acceptability and palatability from Cycle 1 Day 1 (baseline), Cycle 1 Day 15, and Cycle 2 Day 1 will be analyzed.

9.4.10. Biomarker Analyses

Somatic alterations related to treatment, treatment mechanism, and/or cancer may be collected and reported. In addition, the relationship between somatic alterations and clinical outcome may be assessed.

9.5. Interim Analyses

Data will be reviewed on a cohort-by-cohort basis during the study, until the MTDs (not to exceed 115 mg/m² BID) are determined for Parts A and B or CCI [REDACTED]. The purpose of these reviews is to evaluate the safety data at each dose level and determine if a DLT has been

observed that would suggest the MTD for each cohort has been met or exceeded in the dose finding portion. The investigators and Lilly study team will make the determination regarding dose escalation based upon the review of the safety and tolerability data as described in this protocol.

During the dose-expansion portion of each study part, interim analyses may be conducted to review available safety, PK, and efficacy data.

CCI

██████████ DMC will conduct the first interim analysis approximately 2 months (or earlier if deemed appropriate) after Stage 1's last patient begins Cycle 1. If any of the following stopping rules are met or a significant safety signal is identified, the DMC may recommend termination of enrollment, and/or termination of study treatment.

- Rule A: stop for toxicity if ██████ CCI of the DLT-evaluable patients experience DLT.
- Rule B: stop for intolerance if ██████ CCI patients discontinue due to a treatment-related AE before completing ██████ cycles.
- Rule C: stop for insufficient evidence of anti-tumor activity if ██████ of the ██████ patients are responders (i.e., have objective tumor response, including a best overall response of complete response [CR], partial response [PR] or minor response [MR] per INRC).

If 55 mg/m² is declared the MTD, but either Rule A or B is triggered during cohort expansion, the DMC may recommend that subsequent patients be treated at 30 mg/m². See Section 4.1.2.

The DMC will meet and review the overall safety and efficacy data approximately every 6 months thereafter while patients remain in the study. At the recommendation of the DMC, the frequency of safety interim analyses may be modified. See Section 10.1.4 for further details.

Other interim analysis may be added as deemed appropriate by the sponsor.

10. Supporting Documentation and Operational Considerations

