Bone marrow response is determined by cytology (recommended to be accompanied by immunocytoLOGY)/histology (accompanied by immunohistochemistry [Burchill et al. 2017]). Use the bone marrow sample with the highest percentage of tumor infiltration to assess response.

Grading is as follows:

- **Complete Marrow Response**: No tumor infiltration on reassessment, independent of baseline tumor involvement
- **Progressive Marrow Disease**: either
 - bone marrow without tumor infiltration that becomes $> 5\%$ tumor infiltration on reassessment, or

- bone marrow with tumor infiltration that increases by >2 times and has >20% tumor infiltration on reassessment
- **Minimal Disease (MD):** any of the following:
 - $\leq 5\%$ tumor infiltration at baseline and remains > 0 to $\leq 5\%$ tumor infiltration on reassessment, or
 - no tumor infiltration at baseline and $\leq 5\%$ tumor infiltration on reassessment, or
 - $> 20\%$ tumor infiltration at baseline and > 0 to $\leq 5\%$ tumor infiltration on reassessment
- **Stable Marrow Disease:** Persistence of $> 5\%$ tumor infiltration on reassessment that does not meet the criteria for CR, MD, or PD.

Overall response is as follows:

- **Complete Response (CR):** All components meet criteria for CR
- **Partial Response (PR):**
 - PR in ≥ 1 component AND
 - ALL other components are either CR, MD (bone marrow only), PR (soft tissue or bone), or NI (site not involved at study entry remain uninvolved) AND
 - No component with PD
- **Minor Response (MR):**
 - PR or CR in ≥ 1 component AND
 - SD in ≥ 1 component AND
 - No component with PD
- **Stable disease (SD):**
 - SD in ≥ 1 component AND
 - No better than SD or NI (site not involved at study entry and remains uninvolved) AND
 - No component with PD
- **Progressive Disease (PD):** Any component with PD

The overall response based on the combined evaluations is summarized in the table below. The best response observed at any time point for each individual patient will be considered that patient's best overall response on this study.

Primary tumor	Soft tissue or bone metastatic disease	Bone marrow metastatic disease	Overall response
CR	CR	CR	CR
CR for one category and CR or NI for remaining categories			CR
CR	CR	MD	PR
CR	PR	CR	PR
CR	PR	MD	PR
CR	PR	NI	PR
CR	NI	MD	PR
PR	CR	CR	PR
PR	CR	NI	PR
PR	CR	MD	PR

Primary tumor	Soft tissue or bone metastatic disease	Bone marrow metastatic disease	Overall response
PR	PR	CR	PR
PR	PR	NI	PR
PR	PR	MD	PR
PR	NI	CR	PR
PR	NI	NI	PR
PR	NI	MD	PR

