### 7.3.1. *Primary Efficacy Endpoints*

The study was not designed to make an efficacy assessment in Parts A and B, while ORR will be assessed as co-primary endpoint in Part C if a RP2D is achieved. In Part C, ORR is the percentage of patients with a BOR  $\geq$  PR (CR, PR, and MR) per INRC (Park et al. 2017). The response criteria integrate the responses of all lesions using computed tomography/magnetic resonance imaging and/or MIBG/fluorodeoxyglucose-positron emission tomography lesions, and assessment of bone marrow disease. Details are provided in Protocol Section 9.4.6.2.1. All time point responses observed while on study treatment and during short-term follow-up, but before the initiation of post-discontinuation therapy, will be included in the derivation. The primary analysis of response will be based on confirmed responses as defined in [Table JPCS.7.2](#). However, summaries including unconfirmed responses will also be provided. For the interim analysis for Part C, unconfirmed responses may be used.

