**Table JPCS.7.2. Best Overall Response When Confirmation of Responses Required for Part C**

Overall Response First Time Point (1)	Overall Response Subsequent Time Period	Confirmed Best Overall Response
CR	CR ( $\geq$ 28 days from 1)	CR
CR	CR (<28 days from 1)	SD
CR	PR	SD
CR	MR	SD
PR	$\geq$ PR ( $\geq$ 28 days from 1)	PR
PR	$\geq$ PR (<28 days from 1)	SD
PR	MR	SD
MR	$\geq$ MR ( $\geq$ 28 days from 1)	MR
MR	$\geq$ MR (<28 days from 1)	SD
CR/PR/MR	SD	SD
CR/PR/MR	PD	SD if minimum duration of stable disease is met a , otherwise PD

Overall Response First Time Point (I)	Overall Response Subsequent Time Period	Confirmed Best Overall Response
CR/PR/MR	NE/Missing	SD if minimum duration of stable disease is met a , otherwise NE

Abbreviations: CR = complete response; MR = minor response; NE = not evaluable; PD = progressive disease; PR = partial response; SD = stable disease.

a CR/PR/MR occurs at study day >35.

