#### 7.3.2.2. Part C

**BOR:** defined per INRC (Park et al. 2017). Details are provided in Protocol Section 9.4.6.2.1. All time point responses observed while on study treatment and during short-term follow-up, but before the initiation of post-discontinuation therapy, will be included in the derivation. Responses will require confirmation ([Table JPCS.7.2](#)), but where appropriate BOR and endpoints using BOR may also consider unconfirmed responses (for example, interim analysis).

**DoR:** defined only for responders (patients with a CR or MR or PR). It is measured from the date of first evidence of a CR or MR or PR to the date of objective progression or the date of death due to any cause, whichever is earlier.

**DCR:** the percentage of patients with a BOR of CR, MR, PR, or SD.

**CBR:** the percentage of patients with a BOR of CR, MR, PR, or SD for at least 6 months.

**Investigator assessed PFS:** the time from first dose of any drug in study treatment to documented disease progression per INRC or death, whichever occurs first. The Kaplan-Meier method (Kaplan and Meier 1958) will be used to estimate the PFS curves as well as PFS rates at appropriate time intervals (for example, at 3 and 6 months). Detailed censoring rules are provided in Table JPCS.7.3.

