### 7.7.2. Part C

In addition to regular cohort-by-cohort analyses for the dose escalation/de-escalation, an interim analysis for both safety and efficacy is planned for Part C, given that MTD is declared in Stage 1. Specifically, after the MTD is established, an expansion cohort will be enrolled at the MTD to further confirm the tolerability while evaluating the preliminary antitumor activity. In the expansion cohort, up to [REDACTED] patients may be simultaneously enrolled. Stage 1 will enroll up to [REDACTED] DLT-evaluable patients at the identified MTD. The interim analyses will be triggered with data cutoff approximately 1 month (or earlier if deemed appropriate) after the last DLT-evaluable patient begins Cycle 2. If none of the following stopping rules are triggered, the MTD will be confirmed as RP2D, and Part C will move to Stage 2.

- Rule A: stop the trial for toxicity if  $\geq$  [REDACTED] of the DLT-evaluable patients experience DLT.
- Rule B: stop the trial for intolerance if  $\geq$  [REDACTED] patients discontinue due to treatment-related AE before [REDACTED] cycles.
- Rule C: stop for insufficient evidence of anti-tumor activity if  $<$  [REDACTED] of the [REDACTED] patients are responders (that is, have objective tumor response, including a BOR of CR, PR or MR per INRC).

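### Does the Part C futility look come too early for confirmed responses, so that the stated 80% power and 0.025 alpha no longer hold?

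*Protocol*

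**What the plan says.** Part C follows Simon's optimal two-stage design with 80% power and one-sided alpha of 0.025 (Protocol 9.2, SAP 6.3). SAP 6.3 gives 46 patients at the RP2D. The null and alternative rates, the Stage 1 size and both cut-offs are redacted. Stage 2 opens only if Rules A, B and C are all clear (Protocol 4.1.2). Rule C counts patients whose best overall response is CR, PR or MR and does not mention confirmation.

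Protocol 9.5 sets the time of the look: "DMC will conduct the first interim analysis approximately 2 months (or earlier if deemed appropriate) after Stage 1's last patient begins Cycle 1". SAP 7.7.2 places the data cutoff "approximately 1 month (or earlier if deemed appropriate) after the last DLT-evaluable patient begins Cycle 2".

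On which responses count:
- Protocol 8.1 requires a repeat assessment at least 4 weeks after a first CR, PR or MR.
- Protocol 9.4.6.2.1 defines best overall response by "The best response observed at any time point for each individual patient".
- SAP 7.3.1 says of the final test: "The primary analysis of response will be based on confirmed responses". It says of the interim: "For the interim analysis for Part C, unconfirmed responses may be used".
- SAP 7.3.2.2 repeats the allowance: "where appropriate BOR and endpoints using BOR may also consider unconfirmed responses (for example, interim analysis)".
- In SAP Table JPCS.7.2, a response followed by no evaluable scan becomes "SD if minimum duration of stable disease is met" (footnote: "CR/PR/MR occurs at study day >35"), and otherwise NE.

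**The concern.** The look falls between the first scan and the earliest possible confirming scan of the last Stage 1 patient. If Table JPCS.7.2 were applied at the interim, a response on Days 36-42 with no later scan would become SD, because it lies past Day 35. That patient would count as a non-responder under Rule C. If unconfirmed responses count, the same patient is a responder.

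The choice matters because Simon's calculation assumes one fully observed endpoint at both stages. Requiring confirmation makes it easier to stop an active regimen. Counting every unconfirmed response makes it easier for an inactive regimen to reach Stage 2. The SAP says unconfirmed responses may be used, without saying that they will be, and gives no operating characteristics for either count.

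**Working it through.** **Timing (last Stage 1 patient, no delays)**

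- Cycles last 21 days, so Cycle 2 starts on Day 22 and Cycle 3 on Day 43. The scan is due in the week before Cycle 3 (Protocol 1.3.2): Days 36-42.
- Earliest confirmation: 36 + 28 = Day 64 to 42 + 28 = Day 70.
- SAP cutoff: Day 22 + 30 = about Day 52. DMC look: 2 × 365/12 = 60.8, about Day 61.
- Shortfall: 64 − 52 = 12 to 70 − 52 = 18 days at the SAP cutoff; 64 − 61 = 3 to 70 − 61 = 9 days at the DMC look.

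The last patient is therefore always unconfirmed. At an assumed 1-2 starts per month, the number of further patients in the same position is rate × days / 30.4. That is 1 × 12/30.4 = 0.4 to 2 × 18/30.4 = 1.2 at the SAP cutoff, and 1 × 3/30.4 = 0.1 to 2 × 9/30.4 = 0.6 at the DMC look. One or two pending patients is the realistic range.

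**Reproducing the plan's figure**

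The figure of 46 cannot be reproduced uniquely, because the rates are redacted. A search on a 1% grid (null 15-55%, difference 17-30 points) gives 13 Simon-optimal designs with N = 46. Written as null%/alternative%: r1/n1, r, they are: 20/41: 4/16, 14; 22/44: 3/12, 15; 24/46: 4/14, 16; 26/49: 5/15, 17; 36/59: 7/16, 22; 40/63: 7/15, 24; 40/64: 5/11, 24; 42/65: 5/11, 25; 46/68: 7/14, 27; 46/70: 7/13, 27; 48/70: 8/15, 28; 48/71: 7/13, 28; 53/75: 9/15, 30. Their nominal power is 0.801-0.809 and alpha 0.0204-0.0247, in line with the stated 80% and 0.025.

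**Formula**

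Let m Stage 1 patients be pending, with a true (confirmable) responders among the other n1 − m patients and b among the m. G is the number of responders counted at the look. Then

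P(success) = Σa Σb Bin(a; n1 − m, p) × Bin(b; m, p) × P(G > r1 | a, b) × P[Bin(46 − n1, p) > r − a − b].

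The final test always uses true responses. Rule C is treated as binding. The three ways of counting differ only in G:

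1. Confirmation required: G = a.
2. Unconfirmed responses count for all Stage 1 patients: each true responder counts, and each non-responder counts with probability u.
3. Confirmed where known, unconfirmed where pending: G = a + Bin(b, f) + Bin(m − b, u), where f is the share of the pending patients' responses already visible.

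The value u = 0.10 is assumed; the documents give none.

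**One design by hand (40/63: 7/15, 24)**

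The nominal chance of wrongly stopping is P(X ≤ 7 | 15, 0.63) = 0.149. With one patient uncountable it is P(X ≤ 7 | 14, 0.63) = 0.230. Power falls from 0.808 to 0.738. Under count 3 with one pending patient and f = 1, power is 0.812 and alpha 0.0250.

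**All 13 designs**

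| Count at Rule C | Power | Alpha |
|---|---|---|
| Nominal | 0.801-0.809 | 0.0204-0.0247 |
| 1. Confirmation required, m = 1 | 0.702-0.766 | 0.0156-0.0214 |
| 1. Confirmation required, m = 2 | 0.557-0.713 | 0.0104-0.0181 |
| 2. Unconfirmed for all, u = 0.10 | 0.835-0.868 | 0.0237-0.0295 |
| 3. Unconfirmed if pending, m = 1, f = 1 | 0.804-0.814 | 0.0207-0.0250 |
| 3. Unconfirmed if pending, m = 2, f = 1 | 0.807-0.820 | 0.0210-0.0253 |
| 3. Same, m = 1, f = 0.9 | 0.796-0.809 | 0.0202-0.0246 |
| 3. Same, m = 2, f = 0.9 | 0.791-0.810 | 0.0200-0.0247 |
| 3. Same, m = 1, f = 0.8 | 0.787-0.804 | 0.0197-0.0242 |
| 3. Same, m = 2, f = 0.8 | 0.769-0.800 | 0.0190-0.0241 |

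If Rule C never stopped the trial, alpha would be P(X > r | 46, p0) = 0.029-0.036. That is the ceiling for any way of counting.

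**The case for a change.** The strongest case for a change is that the SAP allows a choice and does not make it, in an open-label trial, at the look that opens Stage 2. Under the strict count, one uncountable patient is the minimum, and that alone costs about 4 to 10 points of power. SAP 6.1.2 lets up to 5 patients enrol at once in the expansion, so more than two could be pending.

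The timing and the strict-count losses stand. The strict count, however, is the reading the text supports least. Rule C speaks of best overall response without confirmation, SAP 7.3.1 ties confirmation to the primary analysis, and both SAP sections name the interim as the place where unconfirmed responses may count. Table JPCS.7.2 is headed as applying when confirmation is required and is not linked to Rule C. The rise in alpha under count 2 needs false early responses in all Stage 1 patients, including earlier ones whose repeat scan is already available. Five pending patients at once is a remote case.

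The Day 52 and Day 61 timings are compatible: one is a data cutoff and the other a committee review, and both are approximate.

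A more elaborate remedy would hold Rule C open for every Stage 1 patient still on treatment without progression. That is not cheap. If 30% of the other current non-responders are stable on treatment (assumed), the look is undecided in 57-79% of trials of an inactive regimen with one late patient and in 70-85% with two. At 50% the range is 76-90%. Stable patients have no 4-week repeat scan and would wait for Cycle 4. The trial would often continue with an inactive regimen to guard against a small error.

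**Conclusion.** The concern does not call for a change. The look does precede confirmation for the last Stage 1 patient, but the SAP foresees this by allowing unconfirmed responses there. What remains is missing detail that analysts and the DMC would fill sensibly, with confirmed status where the repeat scan exists and unconfirmed status where it is due. On that reading power is 0.80-0.82 and alpha 0.021-0.025 when all early responses are visible. Alpha passes 0.025 by at most 0.0003. If 20% of the pending patients' responses are not yet visible, power is 0.77-0.80 and alpha stays below 0.025.

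These figures rest on assumptions: 13 illustrative designs in place of the redacted one, one or two pending patients, a 10% rate of early responses that later fail confirmation, and a binding Rule C. Protocol 9.5 says only that the DMC may recommend stopping. Redacted text in Protocol 9.5 or the DMC charter may already fix the count. The conclusion would weaken only if the DMC insisted on confirmed responses for patients who could not yet have them, and nothing in the visible text requires that.

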10.1. Appendix 1: Regulatory, Ethical, and Study Oversight Considerations

10.1.1. Regulatory and Ethical Considerations

- This study will be conducted in accordance with the protocol and with the following:
 - Consensus ethical principles derived from international guidelines including the Declaration of Helsinki and Council for International Organizations of Medical Sciences International Ethical Guidelines
 - Applicable International Council for Harmonisation (ICH) GCP Guidelines
 - Applicable laws and regulations
- The protocol, protocol amendments, ICF, IB, and other relevant documents (e.g. advertisements) must be submitted to an IRB/IEC by the investigator and reviewed and approved by the IRB/IEC before the study is initiated.
- Any amendments to the protocol will require IRB/IEC approval before implementation of changes made to the study design, except for changes necessary to eliminate an immediate hazard to study participants.
- Protocols and any substantial amendments to the protocol will require health authority approval prior to initiation except for changes necessary to eliminate an immediate hazard to study participants.
- The investigator will be responsible for the following:
 - Providing written summaries of the status of the study to the IRB/IEC annually or more frequently in accordance with the requirements, policies, and procedures established by the IRB/IEC
 - Notifying the IRB/IEC of SAEs or other significant safety findings as required by IRB/IEC procedures
 - Providing oversight of study conduct for participants under their responsibility and adherence to requirements of 21 CFR, ICH guidelines, the IRB/IEC, European regulation 536/2014 for clinical studies (if applicable), and all other applicable local regulations
 - Reporting to the sponsor or designee significant issues related to participant safety, participant rights, or data integrity.

After reading the protocol, each principal investigator will sign the protocol signature page and send a copy of the signed page to a Lilly representative.

The CSR coordinating investigator will sign the final CSR for this study, indicating agreement that, to the best of his or her knowledge, the report accurately describes the conduct and results of the study.

10.1.2. Informed Consent Process

- The investigator or his/her representative will explain the nature of the study, including the risks and benefits, to the participant or his/her legally authorized representative and answer all questions regarding the study.
- Participants must be informed that their participation is voluntary. Participants or their legally authorized representative (defined as the participant's parent, guardian, or legal representative) will be required to sign a statement of informed consent that meets the requirements of 21 CFR 50, local regulations, ICH guidelines, Health Insurance Portability and Accountability Act requirements, where applicable, and the IRB/IEC or study center.
- The medical record must include a statement that legally authorized representative (parent/guardian) consent and child/adolescent assent (if deemed appropriate by local ethics review) was obtained before the participant was enrolled in the study and the date the written consent was obtained. The medical record should also describe how the clinical investigator determined that the person signing the ICF was the participant's legally authorized representative (parent/guardian). The authorized person obtaining the informed consent must also sign the ICF.
- Participants and, when applicable, their legally authorized representative (parent/guardian) must be re-consented to the most current version of the ICF(s) during their participation in the study.
- Minor participants must be re-consented if they reach the age of majority during the course of the study, in order to continue participating.
- A copy of the ICF(s) must be provided to the participant, the participant's legally authorized representative, or the participant's parent/guardian when applicable.

Participants who are rescreened and/or their legally authorized representative are required to sign a new ICF and assent, if applicable.

10.1.3. Data Protection

- Participants will be assigned a unique identifier by the sponsor to protect the participant's personal data. Any participant information, such as records, datasets or tissue samples that are transferred to the sponsor will contain the identifier only. Participant names or any information which would make the participant identifiable will not be transferred.
- The participant must be informed that the participant's personal study-related data will be used by the sponsor in accordance with local data protection law. The level of disclosure must also be explained to the participant who will be required to give consent for their data to be used as described in the informed consent. This is done by the site personnel through the informed consent process.
- The participant must be informed through the informed consent by the site personnel that their medical records may be examined by Clinical Quality Assurance auditors or other authorized personnel appointed by the sponsor, by appropriate IRB/IEC members, and by inspectors from regulatory authorities.

- The sponsor has processes in place to ensure information security, data integrity, and data protection. These processes address management of data transfer, and prevention and management of unauthorized access, disclosure, dissemination, alteration or loss of information or personal data. These processes include appropriate contingency plan(s) for appropriate and timely response in the event of a data security breach.
- The transfer of personal data is subject to appropriate safeguards through contractual agreements and processes. The sponsor's processes are compliant with local privacy laws and relevant legislations including the General Data Protection Regulation (GDPR).

